## Impact of lofexidine on stress, craving and opioid use

### A. Significance

**A.1. Opioid Epidemic in Women**. Opioid use disorder (OUDs) are increasing at alarming rates in the United States and the prevalence in women is substantial. While the number of opioid-dependent men in the US remains larger than the number of opioid-dependent women, there are some disturbing trends. Between 1999 and 2015, overdose deaths from prescription pain drugs increased 471 percent in women compared to an increase of 218 percent in men (CDC, 2018). Although nonmedical use of prescription opioids among women has generally been decreasing since 2010 (Jones, 2016), heroin use among women increased faster in women than men and between 2002 and 2013, heroin use among women increased 100% compared to an increase of 50% among men (Cicero et al., 2014). Disturbingly, there has been an enormous increase in the rates of synthetic opioid-related deaths, with an 850 percent increase in deaths for women between 1999 and 2015 (CDC, 2018).

A.2. Gender Differences in Substance Use Disorders (SUDs). There is growing recognition that biological and psychosocial differences between men and women influence the prevalence, presentation, comorbidity and treatment of SUDs. For example, women tend to use smaller amounts of drugs or alcohol for a shorter amount of time before seeking treatment, a phenomenon known as "telescoping" ([name] and Randal, 2007). A similar trend is seen in OUDs; an analysis of data from a multisite clinical trial demonstrated that women progressed to opioid dependence more quickly and experienced more craving as compared to men (Back et al., 2011). Women with SUDs are also more likely to have comorbid depression and anxiety disorders ([name] et al., 1993; [name] and Randall, 1999) and are more likely to attribute use and relapse to negative emotional states and interpersonal conflict (Connors et al., 1998; Back et al., 2011) as compared to men. There is also evidence of gender differences in neurocognitive and brain responses in drug-dependent individuals. An fMRI study examining gender differences in neural correlates of stress- and drug cue exposure found greater corticostriatal-limbic reactivity in cocaine-dependent women during stress exposure, but higher reactivity in these regions during drug cue exposure in cocaine-dependent men suggesting greater neural stress sensitization in women (Potenza et al., 2012). Another study found psychological and emotional distress were identified as risk factors for hazardous prescription opioid use among women, but not men (Back et al., 2011).

**A.3. Stress and Relapse: Sex and Gender Differences**. Etiologic theories of SUDs suggest that stress plays an important role in vulnerability and motivation to abuse addictive substances (Higgins and Marlatt, 1975; Koob and LeMoal, 2001; Russell and Mehrabian, 1975). Animal studies demonstrate that exposure to stress facilitates both initiation and reinstatement of drug use after a period of abstinence (Koob et al., 2004; Stewart, 2000). The brain circuitry (including amygdala and hippocampus) underlying cognitive processing of stress is sexually dimorphic in humans and animals (Kudielka and Kirschbaum, 2005). In addition, hormonal regulation contributes to sexual dimorphism in stress response (Patchev and Almeida, 1998), with estrogen and progesterone acting as modulators of stress regulation (Windle et al., 2006). Corticotropin-releasing factor (CRF), an important mediator of the stress response through the hypothalamic-pituitary-adrenal (HPA) axis and extra-hypothalamic systems, has been implicated in the pathophysiology of stress-induced relapse (Koob et al., 2014). Preclinical studies have demonstrated significant sex differences in CRF systems. For example, female rodents have higher basal levels of CRF in the hypothalamus (Viau et al., 2005; Dunko et al., 2001) and significantly greater adrenocorticotropin hormone (response) to CRF (Kuhn and Francis, 1997).

One focus of our previous SCOR work was the neural circuitry and mechanistic connection between stress and vulnerability to relapse in cocaine dependence. Preclinical studies by our group and others demonstrated that CRF agonists can initiate reinstatement of cocaine-seeking in rodent models (Shaham et al., 2003; Lu et al., 2003). Our SCOR group was the first to demonstrate that female rats are more sensitive to the impact of CRF on cocaine reinstatement compared to male rats (Buffalari et al., 2012). In our human laboratory studies, we found higher subjective stress response and greater HPA axis disruption in cocaine-dependent women compared to men ([name] et al., 2009). Of interest, high stress and craving following CRF administration was associated with higher relapse rates in the month following laboratory testing (Back et al., 2010).

In this same study, the heart rate response following CRF was also more robust and prolonged in women ([name] et al., 2009), suggesting greater noradrenergic activity. Interactions between the brain's noradrenergic and CRF systems are critical to the stress response (Koob et al., 2014; McRae et al., 2017). The noradrenergic system is comprised of two main projections distributed throughout the brain: the dorsal noradrenergic bundle (DNB) originating in the locus coeruleus (LC) and the ventral noradrenergic bundle (VNB) in the brain stem. The noradrenergic receptor system is made up of alpha1, alpha2, and beta receptor subtypes (Berridge and Waterhouse, 2003). Alpha-2 adrenergic agonists, such as clonidine, guanficine and lofexidine, stimulate

inhibitory presynaptic alpha-2 receptors and decrease norepinephrine (NE) cell firing and release centrally (Aghajanian, 1982). Preclinical studies indicate significant sex differences in the LC-NE system, including increased numbers of LC neurons and differences in dendritic structure, so female rats receive more CRF-containing afferents from limbic regions (Bangasser et al., 2016). In addition, estrogen can increase NE in LC target regions by enhancing NE synthesis and reducing degradation (Bangasser et al., 2106). Finally, one study found that CRF was 10–30 times more potent in activating LC neurons in female versus male rats (Curtis et al., 2006).

**A.4. Sex and gender differences in response to noradrenergic agents.** Preclinical evidence suggests that increased NE activity is a mediator of stress-induced reinstatement. Yohimbine, an alpha-2 receptor antagonist that increases NE release, facilitates reinstatement of cocaine (Feltenstein and See, 2006; Lee et al., 2004), methamphetamine (Shepard et al., 2004), and alcohol (Le et al., 2005) seeking. Our SCOR group was the first to demonstrate that female rats were more sensitive to the impact of yohimbine on cocaine-reinstatement than males, with females in proestrus demonstrating the greatest response to yohimbine (Feltenstein et al., 2011). Our SCOR group also demonstrated gender specific sensitivity to noradrenergic dysregulation in cocaine dependence using a human laboratory paradigm. In a double-blind placebo-controlled cross-over study of yohimbine prior to cocaine cue exposure, women reported greater anxiety and craving with yohimbine compared to men (Moran-Santa Maria et al., 2014), suggesting that noradrenergic-mediated stress increased the salience of drug cues for women more than men.

Of interest, alpha-2 agonists selectively block reinstatement of heroin, cocaine, alcohol and nicotineseeking in animal models (Erb et al., 2000; Shaham et al., 2000; Highfield et al., 2001; Yamada and Bruijnzeel, 2011; Le et al., 2005). Several human laboratory studies have also demonstrated that alpha-2 agonists decrease both stress and cue-induced craving in cocaine- and nicotine-dependent individuals (Jobes et al., 2011; Fox et al., 2012; Fox et al, 2014). One investigation of the impact of guanfacine on stress and cue-induced response in cocaine-dependent men and women found that guanfacine significantly attenuated cocaine and alcohol craving, anxiety, and negative emotion in women but not in men (Fox et al., 2014). A Cochrane review found that clonidine treatment for smoking cessation was more effective in women than in men (Gourlay et al., 2004). In a meta-analysis (n = 813) of clonidine studies for smoking cessation, end-of-treatment quit rates in women were 70% for clonidine versus 18% for placebo, whereas men did not demonstrate a medication effect (Glassman et al., 1988). McKee and colleagues (2015) found that guanfacine significantly and equally reduced the number of cigarettes per day following a guit attempt for men and women over a 4-week treatment period. However, guanfacine decreased smoking lapse, cigarettes smoked, and tobacco craving following stress in women but not in men. Although preliminary, these findings suggest that interventions that decrease noradrenergic activity may be more efficacious in reducing substance use in women as compared to men due to sex differences in stress-related sensitization.

**A.5. Opioids, HPA Axis and Noradrenergic Systems**. In opioid dependence, stress system dysregulation is of major significance because of the complex relationships between stress-related neuropeptides (i.e. CRF), the endogenous opioids, and the LC-NE system. The LC-NE system is reciprocally regulated by endogenous opioids and CRF (Curtis et al., 2001; Kawara et al., 2000; Valentino and Van Bockstaele 2001; 2013). Preclinical studies demonstrate that chronic morphine sensitizes the LC-NE system to CRF expressed as increased sensitivity of the neurons to stress, providing a potential mechanism to link opioid use with stress-sensitive disorders (Xu et al., 2004). As detailed above, there is substantial pre-clinical evidence indicating sex differences in these systems, but these differences have not been specifically explored with regard to opioids.

There is some lack of consistency in studies of HPA axis function in opioid dependence. As expected because opioid receptors exert inhibitory control over CRF and HPA axis output, ACTH and cortisol are reduced during heroin exposure and early studies demonstrated normalization of HPA axis function during methadone maintenance (Kreek et al., 2002; Kreek et al., 1983). More recent studies have demonstrated some persistent alterations in HPA axis activity in methadone-maintained individuals, including increased sensitivity to high dose CRH administration (Schulger et al., 2003) and decreased cortisol and CRF levels (Zhang et al., 2009), suggesting suppressed HPA axis function. Although the impact of buprenorphine maintenance on HPA axis function has not been as thoroughly explored, one study using a metyrapone challenge suggested suppressed HPA axis function in individuals on buprenorphine maintenance (Kakko et al., 2008). It is clear, however, that opioid withdrawal engages CRF and other stress-systems, including noradrenergic pathways, and is associated with anxiety and dysphoria (Schulger et al., 2003). Several studies have demonstrated that increased cortisol during opioid withdrawal is positively correlated with opioid craving (Nava et al., 2008; Shi et al., 2009).

A.6. Apha-2 Agonists in Opioid Dependence. Clonidine was the first alpha-2 agonist shown to ameliorate some signs and symptoms of opioid withdrawal (Gold et al., 1978) and is now used in opioid detoxification. Although clonidine is traditionally used only for opioid detoxification, Kowalczyk and colleagues (2015) conducted a randomized double-blind, placebo-controlled relapse prevention trial of adjunctive clonidine treatment in 118 OUD men and women on buprenorphine. The rationale for the trial was based on preclinical reinstatement studies cited above (Erb et al., 2000; Shaham et al., 2000; Highfield et al., 2001). To preserve consistency with the preclinical models, a relapse prevention model requiring a period of abstinence before entering the medication treatment portion of the trial was used as preclinical data suggests that cessation of on-going drug use is mediated by different neural mechanisms than those involved in prevention of relapse (Shalev et al, 2002; Kalivas and Volkow, 2005). Ecologic momentary assessment (EMA) was used during the 14-week trial to query participants about daily life stress and craving. The clonidine-treated group had a significantly longer duration of abstinence as compared to the placebo group. EMA assessment demonstrated that daily life stress was partly decoupled from opioid craving in the clonidine group, supporting the hypothesis that clonidine exerted its beneficial effects by muting the stress response. The number of women in the sample was not large enough to support gender-specific data analysis. Of interest, in studies using a preclinical model of polysubstance abuse, methadone blocked cocaine and heroin-induced reinstatement, but not stress-induced reinstatement (Leri et al., 2004; Sorge et al., 2005).

Lofexidine, also an alpha-2 agonist, has been licensed for opioid detoxification in England since 1992. Three studies and a Cochran review comparing the efficacy and tolerability of lofexidine to clonidine suggest comparable efficacy in reducing withdrawal, with a better risk-benefit profile for lofexidine including better tolerability and less hypotension (Kahn et al., 1997; Lin et al., 1997; Carnwath and Hardman, 1998; Gowling et al, 2016). In a study of 18 opioid-dependent individuals stabilized on naltrexone (NTX), treatment with lofexidine versus placebo was tested (Sinha et al., 2007). During the 4-week treatment period, the lofexidine-NTX patients had higher abstinence rates and improved relapse outcomes as compared to the placebo—NTX group. Ten subjects participated in a human laboratory stress/drug cue exposure paradigm. The lofexidine—NTX patients had significantly lower heart rate and attenuated stress and drug cue response as compared to the placebo—NTX group. The sample size did not support a gender-specific analysis in this study. As in the study by Kowalczyk and colleagues (2015), participants were stabilized on NTX before initiation of study medications, making this a relapse prevention study. Following these two positive clinical studies and based on the preclinical data, we will use a relapse prevention model in this study requiring a period of abstinence before the medication treatment period.

In sum, alterations in the stress response and noradrenergic system are important in pathophysiology of OUD. Alpha-2 agents, which decrease noradrenergic activity, may be helpful in decreasing the stress response in OUD individuals. In cocaine and nicotine dependence, alpha-2 agents have a more robust impact in women as compared to men, however gender differences in OUD individuals have not been explored. The primary objective of this study is to explore gender differences in the impact of an alpha-2 agonist, lofexidine, on the relationship between stress, craving and drug use in individuals with OUDs.

**A.7. Conclusions.** OUDs are increasing at alarming rates in women. Stress and dysregulation in biologic stress response systems appear to play an important role in drug use and the connection between stress and drug use may be particularly important for women. Alterations in CRF, the HPA axis and noradrenergic system are important in the pathophysiology of OUDs and there is evidence that agents that decrease noradrenergic activity may help to prevent relapse and stress reactivity in individuals with OUDs, but gender differences in these effects have not been systematically explored. The primary objective of this study is to explore gender differences in the impact of an alpha-2 agonist, lofexidine, on the relationship between stress, craving and drug use in individuals with OUDs.

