month period. Additional inclusion criteria are consent to random assignment, ability to read and provide informed consent and willingness to remain abstinent from illicit opioids during the 1-week baseline assessment period. Contingency management procedures (described below) will be used to facilitate the maintenance of abstinence during this period. Exclusion criteria are women who are pregnant, nursing, or planning to become pregnant during the course of the study; having a history of or current major psychiatric or medical disorder; hypotension or QTc prolongation on EKG; and meeting criteria for moderate or severe use disorder for another substance with the exception of nicotine. A detailed list of inclusion/exclusion criteria can be found below.

**C.2.b. Recruitment.** MUSC staff will recruit participants from the Charleston Center,, MUSC and community addiction treatment programs, Shoreline Behavioral Health, and through media advertisements As noted in C.1.b., we have a long and successful track record of recruiting from these programs for clinical trials, and the numbers of patients on buprenorphine or methadone maintenance at both sites are more than adequate for recruitment of the required four participants per month to meet the study timeline.

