Substance-Related Instruments. Time Line Follow-back (TLFB; Sobell & Sobell, 1992) is a calendar-based instrument designed to assess daily substance consumption. Opioid use will be recorded in times used per day as well as quantity, type of opioid and route of administration. Urine Drug Screening: Urine samples will be collected and analyzed for prescribed and illicit drugs at baseline and at each study visit. All urine specimens will be analyzed using drug test cups with temperature-controlled monitoring. Drug test cups with immunoassay drug screen cards will be used to identify the following substances: oxycodone, buprenorphine, methadone, tramadol, benzodiazepines, Opiate 300 group analytes (morphine, heroin, and codeine), THC, cocaine, amphetamine, methamphetamine, ethyl glucuronide, fentanyl, K2, and MDMA. Other drugs may be detected by these analytes at high concentrations. For example, hydrocodone may be detected under the oxycodone test at high concentration levels. The cups also include adulterant testing for creatinine, nitrite, pH, bleach and specific gravity. Saliva drug screening: Saliva drug screens will be obtained from Forensic Fluids and will test for THC, cocaine, opiates, benzodiazepines, methadone, oxycodone, buprenorphine, and fentanyl. Patients will collect and store samples which will be returned to the clinic and sent to Forensic Fluids in batches. Samples will be de-identified. Inventory of Drug-Taking Situations (IDTS) (Annis et al., 1997) measures typical drug using situations based on Marlatt and Gordon's (1985) eight category taxonomy. This instrument will be used at baseline and contains eight subscales mapping frequency of use in distinct types of situations including use during negative situations (unpleasant emotions) and positive situations (social situations). Although initially developed for alcohol use, it has been modified for other SUDs and has demonstrated sensitivity to gender

differences (Ross et al., 1994). **Brief Pain Inventory (BPI)** (Cleeland & Ryan, 1994). Assesses severity of pain and impact on functioning. This measure will be completed at screening and at the end of treatment.

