## C.2.c.5. Phase 1: Baseline and Medication Trial

- **a. Initial Study Visit.** Participants will be trained to use CREMA and the one-week naturalistic baseline data collection period will begin following screening procedures. If it is determined that patient is ineligible based on labwork, they will be excluded and baseline procedures will end.
- **b.** Baseline Assessment (Study days 1-7). Throughout this study period, participants will come to the clinic for UDS collection. To facilitate opioid abstinence during the baseline period, we will use a standard contingency-management procedure. Participants will earn payments of \$10 for the first negative UDS and \$20 for the second. Two consecutive UDSs during the baseline week must be negative for illicit opioids in order for the subject to enter the medication treatment part of the trial. During the baseline assessment period, participants will be asked to use CREMA (described below). Subjects may have up to 10 days to provide the negative UDSs.

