Exploratory Aim 3: To evaluate the impact of lofexidine on illicit drug use in men and women with OUDs: Daily use data will be collected through morning reports via EMA and verified by urine drug screens (3 times weekly). Hypothesis 1: Lofexidine will increase the number of consecutive days abstinent as compared to placebo. Hypothesis 2: Lofexidine will be more efficacious in increasing consecutive days abstinent in women as compared to men. Time to relapse will be calculated as the days between the start of study medication (following titration; day 14) and the first day of lapse to opioid use or the laboratory stress induction day (day 40). Additionally, daily use data will be examined to determine the maximum number of consecutive days abstinent during follow up. Kaplan-Meier estimates and log-rank tests will be used to assess initial relationships between study treatment assignment and relapse while Cox proportional hazards models will be developed to assess the differential time to return to use across gender (using and appropriate interaction term). A significant interaction indicates that treatment may impact return to use time differently in women and men. Proportionality of hazards will be assessed using log-log plots and log-time interactions.

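### The design rests on abstinence before medication, but entry needs only two negative urines; recent users can enter and may be counted as relapses in Exploratory Aim 3, where recency of use is not modelled

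*Combined protocol and SAP*

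**What the plan says.** **Rationale.** Section A.6 reports preclinical evidence that "cessation of on-going drug use is mediated by different neural mechanisms than those involved in prevention of relapse". Following two earlier clinical studies, it then states: "we will use a relapse prevention model in this study requiring a period of abstinence before the medication treatment period". It gives no length for that period.

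**Entry.** Section C.2.a asks for "willingness to remain abstinent from illicit opioids during the 1-week baseline assessment period". The general inclusion criteria (item 6) ask for consent to the same. The operative test is in C.2.c.5, item b: "Two consecutive UDSs during the baseline week must be negative for illicit opioids in order for the subject to enter the medication treatment part". The same item adds: "Subjects may have up to 10 days to provide the negative UDSs". On frequency it says only: "Throughout this study period, participants will come to the clinic for UDS collection". Item d makes randomisation follow from the two negative screens.

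**Use data.** The CREMA daily survey asks about substance use over the previous 24 hours and already runs in the baseline week (C.2.c.5, items b and c). The Timeline Follow-back is also listed among the instruments in C.2.c.3. Neither is given a part in the entry decision.

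**Outcome and models.** Under Exploratory Aim 3 in C.2.d: "Daily use data will be collected through morning reports via EMA and verified by urine drug screens (3 times weekly". Time to relapse runs from day 14, which the text describes as coming after titration, to the first lapse or day 40. Kaplan-Meier, log-rank and Cox analyses are named, with a gender-by-treatment interaction. No term for baseline use or recency of use is named, and neither is a stratification factor.

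**The concern.** The protocol uses abstinence before medication to separate two questions: whether lofexidine prevents a return to use, and whether it stops use that is still going on. The entry test separates them only weakly. Someone can use early in the window, give two negative urines a visit apart, and be randomised, even if the daily survey recorded use in between. If that person is still using when the relapse clock starts, the continued use can be recorded as a first lapse.

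A null Aim 3 result could then mean that the drug does not prevent relapse, or that it does not stop ongoing use. Recency of use is also a plausible predictor of early return to use. The trial collects it but names it nowhere in the Aim 3 analysis.

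**Working it through.** The plan states no figure on this point, so there is nothing to reproduce. The check has three parts.

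**1. Entry standard against outcome standard**

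| | At entry | In follow-up |
|---|---|---|
| Urine | Two consecutive negatives | Three times weekly, verifying reports |
| Daily report | Collected, not used | Source of the use data |
| Spacing of screens | None stated | Three visits a week |
| Rule if report and urine disagree | None | None stated |

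C.2.c.5 item d gives three visits a week for induction and throughout the study. If that covers baseline, consecutive screens fall about 7/3 = 2.3 days apart, so roughly 2-3 days. No text makes that interval a condition of entry. C.2.c.3 also notes that "hydrocodone may be detected under the oxycodone test at high concentration levels", so a report of use and a negative urine can coexist, at least for that drug.

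**2. Calendar**

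- Dosing starts on study day 8 and titration runs through day 17.
- The relapse clock starts on day 14, which is titration day 14 - 7 = 7. It is not after titration.
- Days 8-13 are 13 - 8 + 1 = 6 days on study drug before the clock starts, with no scoring rule.
- The clock lasts 40 - 14 = 26 days. From day 18 it would last 40 - 18 = 22.

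**3. Illustrative size**

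From the documents: 136 randomised, 68 per arm. Assumed, with no source in the documents:

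- exponential lapse times;
- 50% of abstinent placebo participants lapse by the end of the clock;
- hazard ratio (HR) 0.5 in abstinent entrants;
- a share f of recent users, equal in both arms in expectation, with hazard k times that of abstinent placebo participants;
- HR in recent users of either 0.5 (drug works equally) or 1 (no effect).

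The abstinent placebo hazard is -ln(1 - 0.5)/T. With the 50% held fixed, T only rescales time, so a 26-day and a 32-day clock give the same results. Each setting was simulated at least 1,500 times and tested two-sided at 5%. The Monte Carlo error on power is about sqrt(0.7 × 0.3/1500) = 1.2 points.

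Unadjusted Cox analysis at f = 10 / 20 / 30%, against HR 0.50 and power 70% at f = 0:

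| Recent users | Estimated HR | Power |
|---|---|---|
| k = 3, drug works equally | 0.51 / 0.52 / 0.53 | 70 / 72 / 74% |
| k = 8, drug works equally | between the rows above and below | 63 / 57 / 52% |
| k = 8, no drug effect | 0.58 / 0.64 / 0.70 | 56 / 44 / 34% |

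As a check at f = 0, Schoenfeld's formula with 68 × (0.5 + 1 - 0.5^0.5) = 53.9 expected events gives 72%.

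The two remedies, same order of f:

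- **Covariate for recent use.** With k = 8 and equal drug effect, power rises from 52-63% to 75-84%. With no drug effect in recent users it does not recover the HR: 0.57 / 0.64 / 0.71.
- **Restriction to abstinent entrants.** With k = 8 and no drug effect in recent users, the HR returns to 0.49-0.50 and power is 65 / 60 / 53%. The sample falls to about 136 × 0.9 = 122, 136 × 0.8 = 109 and 136 × 0.7 = 95.

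The simulation treats recent use as a yes/no variable known without error. Real data will do somewhat worse.

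**The case against.** **Being counted as a relapse is not automatic.** A reader might infer that everyone still using at entry is scored as a relapse at the next report. The plan does not say this. The clock starts on day 14, and on a literal reading someone who stops during days 8-13 would not be scored. What stands is the missing rule for those days and for use already under way at clock start.

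**The contrast between entry and outcome is not urine against self-report.** Follow-up reports are verified by urine, so the asymmetry is partial. The hydrocodone remark is one example. The panel also covers fentanyl, opiates, oxycodone and tramadol, and nothing shows that poorly detected opioids are common here.

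**The baseline week is not lax.** Participants consent to abstain and are paid for negative screens. That should lower the share of recent users, but it does not make abstinence a measured condition of entry.

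**Dilution is conditional.** If lofexidine works equally in recent users and their hazard is only 3-fold, the estimate hardly moves and power does not fall, because there are more events. This stands, and it is why a range is shown.

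**Reach is limited.** Aim 3 is exploratory and the study is powered on Aims 1 and 2. The Aim 1 adjusted models admit unnamed baseline characteristics, and the complete analysis plan is held in the Biostatistics Resource Core. Absence from this text does not prove absence from that plan.

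**Conclusion.** The concern holds for Exploratory Aim 3 and for what can be claimed under the relapse-prevention label. The stated rationale needs prior abstinence. The entry rule secures two negative urines at unstated spacing, sets aside the daily reports, and leaves recency of use out of every named Aim 3 term.

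Randomisation balances recent users between arms in expectation, so the documents do not support a reading of false-positive bias. Nor do they show harm to a primary aim. The exposure is possible dilution and loss of precision. Under the assumptions above, the estimated HR lies between about 0.51 and 0.70, and power between about 74% and 34%, against 0.50 and 70% with no recent users. The share of recent users, their hazard and the drug's effect in them cannot be taken from the documents. The lower end needs both an 8-fold hazard and no drug effect in recent users.

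The gender interaction in Aim 3 would be distorted if recent use differed by sex. The pilot in C.1.c found use on 55.3% of days in women and 30.4% in men in the month after testing (p = 0.107). That is suggestive only and does not measure use at entry.

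**What to change.** Keep the urine gate. In the Exploratory Aim 3 text of C.2.d:

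1. Derive days since last reported illicit opioid use at randomisation from the baseline daily survey and Timeline Follow-back. Include it as a fixed covariate in the Cox models, with its functional form stated in advance.
2. Pre-specify a sensitivity analysis restricted to participants with no reported use from the first qualifying negative urine to randomisation. Both items use only pre-randomisation data, so the randomised comparison is preserved. Both are needed: the covariate recovers precision if the drug works equally in recent users, and restriction recovers the effect in abstinent entrants if it does not.
3. State how use between randomisation and day 14, and use already under way on day 14, is scored, and how a daily report and a urine result combine to define a lapse.
4. Reconcile the day-14 clock start, described as after titration, with titration through day 17.

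In C.2.c.5, state the interval between the two qualifying screens, if one is intended, and whether baseline daily reports bear on entry. If the Biostatistics Resource Core plan already covers any of this, cite it.

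The cost is analysis-plan wording, one derived variable from data already collected and one extra analysis. The downside is fewer participants, and so less power, in the restricted analysis.
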